#### 4.4 Selection of Clinical Sites

UCSF performs approximately 130-140 adult liver transplants for chronic liver disease each year and has had outstanding outcomes based on SRTR data. At the time of protocol design, the median calculated MELD score at transplant is 19.3 (Washburn, 2009) such that approximately 65% would have been eligible based on a calculated MELD score of ≤25 at the time of transplant. However, multiple changes in US liver allocation policy has substantially changed the landscape of liver transplantation. Moreover, throughout the country, the median MELD score at transplant has increased significantly. At UCSF, nearly all subjects who undergo deceased donor liver transplantation across all blood groups with a laboratory MELD score of ≤25 are those who have been granted MELD exception points. The vast majority of these are candidates with HCC which has, historically, accounted for approximately 30-35% of the annual deceased donor liver transplant volume. Exclusion of candidates with active HCV in conjunction with HCC leaves approximately 15% or 20-22 recipients eligible for trial participation annually. Because this trial has additional eligibility assessment steps after enrollment, including donor eligibility for use of cells for a cellular product, we anticipate some attrition at each phase. Therefore, we aim to enroll a minimum of 6-8 patients per year to ensure that 4-5 will progress to darTreg infusion. The pace of enrollment was on par with this plan until October 2015, when the "Wait and Cap" allocation policy for HCC was implemented. The aim of this policy change is to better equalize waitlist mortality of patients with and without HCC. Since the HCC MELD exception score is now capped at 34 and donor livers are regionally shared for candidates with MELD scores ≥35, HCC candidates in Region 5 (UCSF), a region notorious for transplanting at high MELD scores, have much reduced access to transplantation. Our partnership with large transplant centers outside of our region is therefore critical to achieve the enrollment goals for this trial. The UCSF investigators have selected to partner with Mayo Clinic Rochester, Rochester, Minnesota and Northwestern Memorial Hospital, Chicago, Illinois, for many reasons. Mayo Clinic Rochester and Northwestern perform approximately 75-80 and 80-95, respectively, adult liver transplants for chronic liver disease on an annual basis. Both centers are located in United Network for Organ Sharing Region 7 while UCSF is located in Region 5. These two regions differ significantly in the MELD score required to access a deceased donor organ. The lower disease severity at Mayo Clinic Rochester will increase the proportion of transplant recipients eligible to participate in this trial.

In addition to the complementary clinical profile, the most compelling reason for us to partner with both Mayo Clinic Rochester and Northwestern is the breadth and depth of its infrastructure and expertise to support this highly complex trial of a novel therapy. Investigators at Northwestern produce a polyclonal regulatory T cell product which has been administered to living donor kidney recipients to prevent rejection in a Phase I clinical trial (NCT02145325). Both centers are also participating in another clinical trial administering darTreg therapy to facilitate IS withdrawal among adult living donor liver transplant recipients (CTOTC-12/ NCT02474199). Participation in two trials involving the same product in a similar patient population will substantially increase their familiarity with the study procedures and processes and enhance their ability to conduct the proposed trial with high fidelity. The combined infrastructure supporting both trials will escalate the commitment to the proper collection, processing, and shipment of samples for both darTreg manufacturing and for the accompanying mechanistic assays.

Confidential Page 35 of 80

#### 5. Investigational Agents

#### 5.1 Deuterium-labelled darTreg Product

The darTreg product will be manufactured at Human Islet and Cellular Transplantation Facility (HICTF) and GMP Facility: [name]
[name]
San Francisco, CA 94103

#### 5.1.1 Manufacturing, Formulation, Packaging, and Labeling

#### Recipient T cell Banking

Peripheral blood leukocytes will be collected via leukapheresis from participants enrolled into Cohorts 3 and 4 after successful screening and prior to transplantation. Cohort 2 subjects might have leukapheresis or whole blood collection for PBMC isolation. The whole blood or leukapheresis product will be transported to the manufacturing facility. PBMCs will be isolated using Ficoll density gradient centrifugation and cryopreserved in liquid nitrogen until the patient is eligible for darTreg infusion. If HBV DNA is greater than 1,000 IU/mL at the time of PBMC collection, then the resulting PBMC product will not be utilized to manufacture darTregs. At least 2x10^9 PBMCs (leukapheresis) or 2x10^8 PBMC (whole blood) are expected to be collected and banked from each subject. If the whole blood or leukapheresis product does not contain sufficient numbers of Tregs, phlebotomy or leukapheresis can be repeated to ensure an adequate cell number for product manufacture before transplant.

#### Donor B cell (sBcs) Banking and Activation

On the day of transplantation, donor spleen and/or whole blood will be collected and transported to the manufacturing facility for processing into a single cell suspension followed by stimulation and expansion with irradiated KT64-CD40L.HLADR0401 cells and expanded for 10 days in the presence of recombinant human IL-4, cyclosporine A and ganciclovir. The CD40L-stimulated donor sBcs will be sorted, irradiated, and cryopreserved until needed for darTreg expansion. Failure to collect donor cells will disqualify a subject from further trial participation for participants in Cohorts 2, 3, or 4. Participants in Cohorts 1a and 1b will be allowed to continue in the trial since they are not scheduled to undergo darTreg infusion.

#### **Treg Expansion**

The banked recipient PBMCs will be thawed, washed, stained and sorted for CD4+127lo/-25+ Tregs. Purified Tregs will be cultured with irradiated sBcs at a ratio of 4:1 in deuterated media. On day 11, cells will be further stimulated with beads conjugated with anti-CD3 and anti-CD28 mAbs-conjugated beads at a 1:1 ratio. Beads will be removed and the appropriate number of cells will be counted and re-suspended in 100 mL of infusion media (see below) at the appropriate concentration, and aseptically filled in infusion bags. The final product will be quarantined at 4°C until release.

Each lot will be released for infusion if it meets the pre-defined specifications criteria, including  $\geq$ 95% CD4+,  $\geq$ 60% FOXP3+,  $\geq$ 75% TSDR+,  $\leq$ 5% CD8+,  $\leq$ 1% CD19+.

#### 5.1.1.1 darTreg Formulation, Packaging and Labeling

The deuterium-labelled darTreg product is fresh, non-cryopreserved, sterile cell suspension of  $\geq$ 85% viable,  $\geq$ 95% CD4+,  $\geq$ 60% FoxP3+-, cells for IV administration of a single dose containing 50 (range: 25-60 x 10^6 cells ), 200 (range: 100-240 x 10^6 cells ) or 800 x 10^6 (range: 400-960 x 10^6 cells) darTregs and formulated in 100 mL of sterile infusion solution containing 49.02% (v/v) PlasmaLyte-A USP, 49.02% (v/v) Dextrose 5%-USP, 0.45% NaCl-USP, and 1.96% (v/v) 25% human serum albumin. The product is supplied in a sterile, PVC, 150-mL infusion bag (Charter Medical catalog #T3000). The final product should be stored and maintained at 2-10°C until ready to use.

The product will be released with an interim Certificate of Analysis (COA). The final COA will be provided once the sterility results become available.

#### 5.1.2 Dosage, Preparation, and Administration

Confidential Page 36 of 80

The deuterium-labelled darTreg product will be transported within UCSF and between UCSF and remote clinical centers in a shipping container with a temperature monitor and a coolant pack(s) to maintain the temperature between 2°C and 10°C. The product should be maintained in the shipping container until its administration. The infusion of the product must occur within 30 hours after final formulation. The identity of the donor, recipient and the product will be verified by two individuals prior to infusion.

Subjects meeting eligibility criteria for darTreg infusion will receive a single IV dose containing 50 (range 25-60), 200 (range 100-240), or 800 (range 400-960) million darTregs administered in approximately 20-30 minutes by gravity. The line will be primed with saline prior to infusion and the product bag, tubing, and peripheral IV line will be flushed with up to 250ml normal saline to ensure the complete dose is infused.

Pre-medications will be administered prior to infusion (see Section 6.2.2).

Vitals signs will be monitored before, during, and after the infusion. Emergency medical equipment will be available during the infusion in case the subject has an allergic response or an infusion reaction that can result in a CRS. The IV line will be maintained after the infusion and the subject will be asked to remain in the clinical research unit for a minimum of 24 hours which will allow ongoing monitoring for any infusion-related signs and symptoms.

#### 5.1.3 Repeated darTregs Manufacturing

The manufacturing process can be repeated once for a particular subject if there or technical or logistical issues with the first preparation. The study team will review the available manufacturing information to determine if a second manufacturing attempt is likely to be successful. Except for liver biopsy, the laboratory components of Screen D must be repeated within 10 days of planned infusion to ensure eligibility. In any case, infusion of darTregs must take place no later than 20 weeks after transplantation. If the second attempt at manufacturing fails, the subject will go into safety follow up (Appendix 4).

#### 5.2 Thymoglobulin® (Anti-Thymocyte Globulin – Rabbit)

Thymoglobulin® (ATG) is manufactured by Genzyme Corporation (Cambridge, MA). Generic forms of the medication are also available but, for this trial, generic formulations should not be used. Thymoglobulin® is licensed for the treatment of renal transplant AR in conjunction with concomitant IS. Currently, there is no indication for the use of Thymoglobulin® as an induction therapy in the context of liver transplantation. Data from the Scientific Registry of Transplant Recipients, however, shows that there has been an increasing trend for liver transplant recipients to be treated with induction therapy over the past 10 – 15 years. In 1999, approximately 13% of liver transplant recipients received induction therapy with less than 2% receiving a polyclonal agent (Thymoglobulin® or ATGAM). By 2008, nearly 30% of liver transplant recipients received induction therapy with approximately 14% receiving a polyclonal, T cell depleting agent (Thymoglobulin® or ATGAM). Interest in using Thymoglobulin® has been driven by multiple motivations including the desire to reduce or even eliminate exposure to corticosteroids and to delay and / or minimize exposure to CNIs in an attempt to reduce nephrotoxicity and optimize short and long-term renal function. Hence, T cell depletion is already an accepted approach to IS in liver transplant patients.

For this trial, we have chosen to administer a course of Thymoglobulin® within 72 hours after transplantation with the goal of achieving adequate lymphocyte depletion. We have chosen a dose range, 3.0-4.5 mg/kg that balances the desire for depletion with hematologic side effects of Thymoglobulin® administration. This dose range has been shown to be as effective at depleting T cells as compared to the more common 6 mg/kg dosing (Wong, 2008). Moreover, immunologic outcomes appear to be indistinguishable between dose ranges (Wong, 2008). Dose dependent leukopenia and thrombocytopenia will be minimized by using lower doses, which will be particularly important for liver transplant patients who have depressed leukocyte and platelet counts at baseline.

#### 5.2.1 Formulation, Packaging, and Labeling

Thymoglobulin® is a purified, preservative-free, pasteurized, gamma immune globulin, obtained by immunization of rabbits with human thymocytes. Thymoglobulin® is available as sterile, lyophilized powder to be reconstituted with sterile water for Injection (SWFI). Each package contains a 10 mL vial of freeze-dried Thymoglobulin® (25 mg) NDC# 58468-

Confidential Page 37 of 80

0080-1. Each 10 mL vial contains 25 mg anti-thymocyte globulin (rabbit) as well as 50 mg glycine, 50 mg mannitol, and 10 mg sodium chloride. After reconstitution with 5 mL SWFI, each vial of reconstituted product contains approximately 5 mg/mL of Thymoglobulin®, of which >90% is rabbit gamma immune globulin (IgG). The reconstituted solution has a pH of 6.5 - 7.2.

Vials should be stored in a refrigerator at 2°C to 8°C (36°F to 46°F) and protected from light. The vials should not be frozen and should not be used after the expiration date indicated on the label. Reconstituted Thymoglobulin® is physically and chemically stable for up to 24 hours at room temperature; however, room temperature storage is not recommended. As Thymoglobulin® contains no preservatives; the reconstituted product should be used immediately. Any unused drug remaining after infusion must be discarded.

## 5.2.2 Dosage, Preparation, and Administration (Package Insert)

# Reconstitution

After calculating the number of vials needed, using aseptic technique, reconstitute each vial of Thymoglobulin® with 5 mL of SWFI.

- 1. Allow Thymoglobulin® vials to reach room temperature before reconstituting the lyophilized product.
- 2. Aseptically remove caps to expose rubber stoppers.
- 3. Clean stoppers with germicidal or alcohol swab.
- 4. Aseptically reconstitute each vial of Thymoglobulin® lyophilized powder with the 5 mL of SWFI.
- 5. Rotate vial gently until powder is completely dissolved. Each reconstituted vial contains 25 mg or 5 mg/mL of Thymoglobulin®.
- 6. Inspect solution for particulate matter after reconstitution. Should some particulate matter remain, continue to gently rotate the vial until no particulate matter is visible. If particulate matter persists, discard this vial.

#### Dilution

- 1. Transfer the contents of the calculated number of Thymoglobulin® vials into the bag of infusion solution (saline or dextrose). Recommended volume: per one vial of Thymoglobulin® use 50 mL of infusion solution (total volume usually between 50 to 500 mL).
- 2. Mix the solution by inverting the bag gently only once or twice

#### Dosage and Administration

[figure not shown]
The recommended dosage of Thymoglobulin® for treatment of acute renal graft rejection is 1.5 mg/kg of body weight administered daily for 7 to 14 days.

The recommended route of administration is intravenous infusion using a high-flow vein. Thymoglobulin® should be infused over a minimum of 6 hours for the first infusion and over at least 4 hours on subsequent days of therapy. Thymoglobulin® should be administered through an in-line 0.22 micrometer filter.

### 5.2.3 Thymoglobulin® Study Dosing and Administration

[figure not shown]
For this study, subjects will be given a dose range of 3.0-4.5 mg/kg total. Subjects who meet eligibility criteria for Thymoglobulin® will be given the first dose no later than 72 hours after transplantation. For transplants occurring during overnight hours, the first dose might begin on Day 2.

The first and second doses of Thymoglobulin® must be 0.75 mg/kg administered over 12 hours. Additional doses of 0.75 -1.5 mg/kg IV will be administered over 6-12 hours, or at the site investigator's discretion, until CD3 count is less than or equal to 50 cells/ $\mu$ L (50 cells/mcL) or total lymphocyte count is less than or equal to 0.10 x 10 $^9$ /L when CD3 count is unavailable; or when the maximal dose of 4.5/mg/kg has been given.

Note: If Myfortic is used, dosing should be 360 mg BID.

Figure 9. EVR-based Regimen after Thymoglobulin®

Note: If Myfortic is used, dosing should be 360 mg BID.

Figure 10. TAC-based Regimen after Thymoglobulin®

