# Treatment Description

#### Treg-supportive IS regimen:

- Rabbit anti-thymocyte globulin (Thymoglobulin®) induction (3-4.5 mg/kg started by day 3)
- Corticosteroids (500 mg intra-operatively, taper to off by week 5)
- Mycophenolate mofetil (1000 mg total daily dose)
- TAC, with target trough level of 6-8 μg/dL

Between 30 and 44 days following transplant: Subjects who are not eliminated by Exclusion Criteria C1 (Section 4.3.3) will proceed in the study and receive either TAC-based or EVR-based IS, based on eligibility Criteria C2 (Section 4.3.4)

- TAC-based IS: reduce TAC trough level to 3-8 μg/dL; continue MMF
- EVR-based IS: reduce TAC trough level to 3-5 μg/dL; EVR target trough level of 6-8 μg/dL; decrease then discontinue MMF

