#### 4.3.3 Exclusion Criteria C1

Below are exclusion criteria to be assessed at day 30-44 after transplantation for continuation in the trial. All subjects regardless of eligibility for EVR conversion, with any of the following will not receive darTregs and will move into safety follow up.

- 1. Explanted liver with evidence of increased risk of recurrent cancer (HCC tumor burden exceeding the Milan criteria; presence of vascular invasion; cholangiocarcinoma morphology)
- 2. Insufficient depletion of recipient T cells, defined as a nadir CD3 count ≥50 cells/µL (50 cells/mcL) or total lymphocyte count ≥ 0.1 x 10^9/L if CD3 count is unavailable
- 3. Development of a condition requiring chronic anti-coagulation
- 4. Clinical evidence of untreated biliary obstruction
- 5. ALT >2.0 x upper limit of normal (ULN)
- 6. Inability to taper off corticosteroids by 44 days (+/- 2 days) after transplant
- 7. Detectable circulating HCV

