### 7. Premature Discontinuation of Investigational Therapy

# 7.1 Premature Discontinuation of Thymoglobulin and/or Treg Supportive IS Regimen

Study IS regimen may be prematurely discontinued for any participant for any of the following reasons:

- 1. Inability to tolerate at least 3 mg/kg Thymoglobulin® or inability to deplete CD3 count to less than or equal to 50μ/L (50/mcL) or total lymphocyte count to less than equal to 0.1 x 109/L after study Thymoglobulin® administration
- 2. Inability to tolerate TAC- or EVR-based maintenance IS
- 3. The diagnosis of severe AR (Banff criteria) at any time after transplantation
- 4. The diagnosis of early or late CR (Banff criteria) at any time after transplantation
- 5. The occurrence of steroid refractory rejection at any time after transplantation
- 6. Poor compliance with study procedures.
- 7. Investigator decision that the study IS regimen and/or future study treatment is no longer in the best interest of the participant.
- 8. Failure to manufacture and supply the cellular product two times for the same subject

There are a myriad of diagnoses that might lead an investigator to determine that the study IS regimen and/or darTreg infusion is no longer in the best interest of the participant. While there are likely an infinite number of specific reasons, general reasons include severe, life-threatening infections, malignancy (excluding skin cancer), GvHD, pneumonitis, severe renal dysfunction / proteinuria, serious medical co-morbidity such as myocardial infarction, and logistical issues including patient relocation and record of non-compliance.

The (Data Safety Monitoring Board) DSMB will be provided with information about cases of premature discontinuation occurring in any stage. Subjects who have prematurely discontinued the study regimen will enter into a schedule of events (SOE) of reduced monitoring intensity for purpose of safety (Please refer to Section 13.4 and Safety Follow-Up SOE)

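### The Thymoglobulin stop rule carries no minimum dose, and Protocol 5.2.3, 7.1, Appendix 1 and criterion C1 do not define T-cell depletion in the same way

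*Protocol*

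**What the plan says.** **Total dose.** Protocol 5.2.3 states that "subjects will be given a dose range of 3.0-4.5 mg/kg total". The synopsis (Treatment Description), section 5.2 and the Thymoglobulin row of Appendix 1 give the same range.

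**Dosing steps.** Still in 5.2.3: "The first and second doses of Thymoglobulin® must be 0.75 mg/kg administered over 12 hours". Then: "Additional doses of 0.75 -1.5 mg/kg IV will be administered over 6-12 hours, or at the site investigator's discretion". These continue "until CD3 count is less than or equal to 50 cells" per µL, "or total lymphocyte count is less than or equal to 0.10 x 10"^9/L when no CD3 count is available, or until 4.5 mg/kg has been given. Appendix 1 footnote 10 repeats the stop rule, also without a minimum, and omits the condition that CD3 be unavailable.

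**Eligibility to continue.** Criterion C1 no. 2 (section 4.3.3 and the synopsis) excludes for "Insufficient depletion of recipient T cells, defined as a nadir CD3 count" of 50 cells/µL or more, or lymphocytes of 0.10 x 10^9/L or more if CD3 is unavailable. A subject who meets any C1 criterion gets no darTregs and enters safety follow-up.

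**Discontinuation.** Section 7.1 lists, among reasons for which the regimen may be stopped, "Inability to tolerate at least 3 mg/kg" of Thymoglobulin, or failure to bring CD3 to 50 or below or lymphocytes to 0.1 x 10^9/L or below. It does not limit the lymphocyte criterion to cases without a CD3 count.

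**The concern.** Depletion status decides both when Thymoglobulin stops and who may go on to darTregs. If the sections that define it disagree, two sites can treat the same count differently and each can point to the protocol.

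The rationale in 5.2 is attached to 3.0-4.5 mg/kg, so a total below 3.0 falls outside the range that the protocol justifies. A C1 exclusion comes after the patient has already been lymphodepleted. Cohorts 2 and 3 plan three infused subjects each, and 15.3 sends the replacement of Thymoglobulin-treated subjects who do not receive darTregs to the review in 13.3. The choice of section also decides who contributes person-weeks to the darTreg analysis period (Protocol 15.4.1, SAP section 5) and who appears in the screen-failure summary (SAP 5.1).

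**Working it through.** **1. Totals that the dosing steps can produce**

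Inputs, all from 5.2.3: two fixed doses of 0.75 mg/kg; further doses of 0.75 to 1.5 mg/kg; cap 4.5 mg/kg. Total after k doses = 2 x 0.75 + (k - 2) x d, with d between 0.75 and 1.5, capped at 4.5.

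| Depletion target first met after | Lowest total (mg/kg) | Highest total (mg/kg) |
|---|---|---|
| dose 2 | 2 x 0.75 = 1.5 | 1.5 |
| dose 3 | 1.5 + 0.75 = 2.25 | 1.5 + 1.5 = 3.0 |
| dose 4 | 1.5 + 2 x 0.75 = 3.0 | 1.5 + 2 x 1.5 = 4.5 |
| dose 5 | 1.5 + 3 x 0.75 = 3.75 | 4.5 (cap) |
| dose 6 | 1.5 + 4 x 0.75 = 4.5 | 4.5 (cap) |

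The plan's upper limit of 4.5 is reproduced. Its lower limit of 3.0 is not: the steps allow 1.5 to 4.5, and 1.5/3.0 = 50% of the stated minimum. After three doses the total is below 3.0 unless the third dose is the full 1.5.

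**2. The inequalities at the boundary**

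The lymphocyte rows assume that CD3 is unavailable and that the value shown is the lowest recorded.

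| Value | Stops dosing (5.2.3, footnote 10) | Depletion failure under 7.1 | Excluded by C1 |
|---|---|---|---|
| CD3 49 | yes | no | no |
| CD3 50 | yes | no | **yes** |
| CD3 51 | no | yes | yes |
| Lymphocytes 0.09 | yes | no | no |
| Lymphocytes 0.10 | yes | no | **yes** |
| Lymphocytes 0.11 | no | yes | yes |

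The conflict sits at equality only. C1 uses the nadir, so a subject stopped at CD3 50 is excluded only if no other CD3 count is lower.

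**3. When lymphocytes may be used**

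0.10 x 10^9/L = 100 cells/µL. Take a subject with lymphocytes of 90/µL and a measured CD3 of 60/µL, with 60 the lowest CD3 recorded and less than 4.5 mg/kg given:

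- Footnote 10: 90 is at or below 100, so dosing stops.
- 7.1: not a depletion failure, if reaching either target is enough.
- 5.2.3: CD3 is available and above 50, so more doses are due.
- C1: CD3 is available and at least 50, so the subject is excluded.

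This mismatch does not need an exact tie. It applies to any measured CD3 above 50 with lymphocytes at or below 100/µL.

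**4. How wide the lymphocyte tie is**

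This depends on reporting precision, which the documents do not give. If two decimals are reported (assumption), true values of about 0.095 to 0.105 read 0.10. If one decimal (assumption), about 0.05 to 0.149 read 0.1, a band roughly ten times as wide.

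**The case against.** Every place that states a total gives 3.0 as the lower end, and none says that dosing may stop at 1.5. The stop rule can be read as adjusting the dose within the stated range: two fixed doses plus two further doses give exactly 3.0 to 4.5. That reading is reasonable and would remove the dose conflict. However, the text does not fix the number of further doses and does not say that the target applies only after 3.0. What stands of the objection is that a precedence clause is missing; the protocol does not instruct sites to underdose.

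Three stronger inferences are tempting and are not supported:

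- *Meeting the stop criterion leads to exclusion in general.* It does not. Any CD3 below 50 ends dosing and passes C1, and the nadir rule can rescue a subject stopped at exactly 50. The rescue needs another count: Appendix 1 appears to schedule CD3 only on Days 2 to 6 (Days 2 and 6 only if Thymoglobulin is given then) and CD4 at Screen C.
- *Section 7.1 makes a subject who stops early because depleted a candidate for discontinuation.* Its 3 mg/kg clause concerns tolerance, and the list is permissive. It leaves that subject's status open.
- *The lymphocyte tie spans 0.05 to 0.149.* That needs one-decimal reporting. Section 5.2.3, footnote 10 and the synopsis version of C1 write 0.10, which points towards two decimals, while 4.3.3 and 7.1 write 0.1. This route also opens only when CD3, a scheduled test, is missing.

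The wording of 7.1 also bears a second reading, in which missing either target is a failure. The example in step 3 would then fail 7.1, but the conflict of footnote 10 with 5.2.3 and C1 would remain.

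**Conclusion.** The concern holds for the wording, in three parts. First, 5.2.3 and footnote 10 set no minimum, so the literal steps allow totals of 1.5 mg/kg or 2.25 to 3.0 mg/kg against a stated 3.0, and nothing says which statement governs. Second, at exact equality the same count is depleted in 5.2.3, 7.1 and footnote 10 and insufficiently depleted in C1. Third, footnote 10 and 7.1 drop the condition on using lymphocytes, which extends the disagreement beyond equality.

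The first part rests on a literal reading of the stop rule. The 7.1 element of the third rests on reading its or as either target sufficing. Frequency cannot be derived: the documents do not say how often depletion is reached within three doses, how often a nadir falls on the threshold, or how often CD3 and lymphocytes point in different directions. With dose cohorts as small as three, one subject handled inconsistently would still be noticeable.

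**What to change.** Reconcile the synopsis (Treatment Description and criteria C1), 4.3.3, 5.2, 5.2.3, 7.1, and the Thymoglobulin row and footnote 10 of Appendix 1, so that:

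1. the dosing target, the depletion criterion in 7.1 and C1 use one inequality, for CD3 and for lymphocytes;
2. all of them use one condition for when lymphocytes may stand in for CD3;
3. the text states whether the total-dose range or the depletion target governs when they disagree, and how a subject who reaches the target below the stated range is classified;
4. the lymphocyte threshold is written to one stated precision.

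Which dose rule and which inequality apply is for the sponsor to decide. The cost is protocol wording only. Changing 5.2.3, 7.1 and 4.3.3 alone would leave the synopsis and footnote 10 open to conflict with the new text.
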